14.0 Resources and Qualifications

14.1 Describe the qualifications (e.g., education, training, experience, expertise, or certifications) of the Principal Investigator and staff to perform the research. When applicable describe their knowledge of the local study sites, culture, and society. Provide enough information to convince the IRB that you have qualified staff for the proposed research.

NOTE: If you specify a person by name, a change to that person will require prior approval by the IRB. If you specify a person by role (e.g., coordinator, research assistant, co-investigator, or pharmacist), a change to that person will not usually require prior approval by the IRB, provided that the person meets the qualifications described to fulfill their roles.

Response:

[name] is the chief of endocrinology division and a distinguished professor of University at Buffalo. He has published multiple articles in the field of obesity. Staff members at our research unit at Erie County Medical Center are well trained to conduct this type of research. Further, all study personnel are educated, trained, and licensed as required for their delegated role in this study. All study personnel have also received the required university training and will be trained by the PI before the study starts

[name] is an expert in transcranial direct current stimulation. He will provide transcranial direct current stimulation device, computer tasks and questionnaires training. He will also review the protocol and participate in manuscript preparation. He and his staff at Harvard university has trained and will continue to train our staff if there is a need.

Describe other resources available to conduct the research.

14.2 Describe the time and effort that the Principal Investigator and research staff will devote to conducting and completing the research.

NOTE: Examples include the percentage of Full Time Equivalents (FTE), hours per week. The question will elicit whether there are appropriate resources to conduct the research.

Response:

The principal investigator supervises the research project and weekly research meetings are conducted to discuss the recruitment rate, resolve and discuss issues related to the conduct, safety, analysis of the study and related publications. PI is expected to spend 5% of his academic time on this research. The co-investigators and study coordinator provide coverage to the research related activity for 365 days a year.

14.3 Describe the availability of medical or psychological resources that subjects might need as a result of anticipated consequences of the human research, if applicable.

NOTE: One example includes: on-call availability of a counselor or psychologist for a study that screens subjects for depression.

Response:

Available medical literature will be provided as deemed appropriate or requested by patient through UB libraries, Pubmed, Google scholar as all the investigators have access to medical literature through listed resources above

The patient will also have access to physician (Investigators and Co-Investigators) who will be available to address any adverse effects or other questions during the course of the study

14.4 Describe your process to ensure that all persons assisting with the research are adequately informed about the protocol, the research procedures, and their duties and functions.

Response: Education through meetings, conferences and discussions

15.0 Other Approvals

15.1 Describe any approvals that will be obtained prior to commencing the research (e.g., school, external site, funding agency, laboratory, radiation safety, or biosafety).

Response:

N/A: This study does not require any other approvals.

16.0 Provisions to Protect the Privacy Interests of Subjects

16.1 Describe how you will protect subjects' privacy interests during the course of this research.

NOTE: Privacy refers to an individual's right to control access to him or herself. Privacy applies to the person. Confidentiality refers to how data collected about individuals for the research will be protected by the researcher from release. Confidentiality applies to the data.

Examples of appropriate responses include: "participant only meets with a study coordinator in a classroom setting where no one can overhear", or "the participant is reminded that they are free to refuse to answer any questions that they do not feel comfortable answering."

Response:

Patients who agree to be contacted for potential participation in a research study will have their information given to the research coordinator to be contacted.

Participant will arrive at the Diabetes Endocrinology Research Center of WNY, and will be placed in a private area to review the consent. They will be allowed to address their question and concerns in private with the research coordinator, study nurse and/or research physician. At any time during the study the patient is able to place privacy restriction to their protected health information (i.e. telephone message, PHI release forms) which the study personnel document and respect.

Additionally, when patients are seen in the clinic for the first time they sign the “Consent to use and disclosure of protected health information”. This form clearly states that their protected health information (PHI) can be used for review in preparation for possible research.

We will not be accessing any medical information of the patients for whom the services are not provided by our clinic providers

16.2 Indicate how the research team is permitted to access any sources of information about the subjects.

*NOTE: Examples of appropriate responses include: school permission for review of records, consent of the subject, HIPAA waiver. This question **does apply** to records reviews.*

Response: Consent of the subject and HIPAA waiver.

17.0 Data Management and Analysis

17.1 Describe the data analysis plan, including any statistical procedures. This section applies to both quantitative and qualitative analysis.

Response:

The demographic features of the population and screening lab results will be displayed in tables. Statistical analysis will be conducted using SigmaStat software version 3.1 (SPSS Inc., Chicago, IL). Data will be represented as mean \pm S.E. Sample size cannot be estimated as this is a pilot study. Generalized linear mixed model will be applied to compare the difference in weight, average amplitude of glucose excursion curve, average daily meal count, HOMA-IR, reaction time and percentage correct response in computerized cognitive tests. Predicting variables include time in the study (baseline, visit 5 and visit 6) and type of intervention (active tDCS vs sham). Sensitivity analysis will be performed to evaluate baseline imbalance, outliers, protocol violation, and missing data. The proposed covariants to be evaluated for baseline imbalance includes age, gender, COMT and BDNF gene status, baseline weight, baseline HOMA-IR, baseline average amplitude of glucose excursion curve, baseline average daily meal count, baseline reaction time and percentage correct response.

17.2 If applicable, provide a power analysis.

NOTE: This may not apply to certain types of studies, including chart/records reviews, survey studies, or observational studies. This question is asked to elicit whether the investigator has an adequate sample size to achieve the study objectives and justify a conclusion.

Response: This is a pilot study, so we are not able to estimate sample size. However, previous shorter term study showed a small effect of tDCS on appetite and weight (see reference 9) in nine patients. We consider that by recruiting 20 participants, it will be more likely to detect a significant change, while the total expense will still be within the limit of our fund.

17.3 Describe any procedures that will be used for quality control of collected data.

Response:

Date entered by research staff will be verified by another person independently.

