1.0 Objectives

1.1 Describe the purpose, specific aims, or objectives of this research.

Response: To study the effects of transcranial direct current stimulation (tDCS) on weight and appetite.

Aim:

- 1. To compare weight loss over one month in active tDCS group with sham tDCS group. We will measure weight of every participants at the beginning of the study and one month after the last session of tDCS*
- 2. To compare change in insulin sensitivity over one month in active tDCS group with sham tDCS group. We will measure fasting insulin and glucose level, and calculate homeostatic model assessment-insulin resistance (HOMA-IR)*
- 3. To compare change in cognitive performance as a response to food over one month in active tDCS group with sham tDCS group. We will evaluate performance in a computerized task that measures executive functions under the presence of food (working memory, inhibitory control and a combination of both). We will assess changes in accuracy and speed in the task under active tDCS versus sham tDCS.*
- 4. To compare change in post-prandial glucose excursion and average meal counts per day. We will use continuous glucose monitor to record the frequency and amplitude of glucose excursion.*

1.2 State the hypotheses to be tested, if applicable.

NOTE: A hypothesis is a specific, testable prediction about what you expect to happen in your study that corresponds with your above listed objectives.

Response:

Hypothesis:

- 1. Active tDCS will result in more weight loss, appetite reduction and improved insulin sensitivity compared with sham tDCS over one month period.*
- 2. The effect of tDCS on weight, appetite, glucose tolerance and cognitive response to food varies according to the underlying allele status of BDNF and COMT gene*

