2.0 Scientific Endpoints

2.1 Describe the scientific endpoint(s), the main result or occurrence under study.

*NOTE: Scientific endpoints are outcomes defined before the study begins to determine whether the objectives of the study have been met and to draw conclusions from the data. Include primary and secondary endpoints. Some example endpoints are: reduction of symptoms, improvement in quality of life, or survival. Your response should **not** be a date.*

Response:

Primary endpoints: change in weight, measured as a percentage of baseline body weight.

Secondary endpoints: change in HOMA-IR, change in average daily meal counts based on frequency of glucose excursion on continuous glucose monitor, change in average amplitude of glucose excursion curve after meals, change in cognitive performance in response to food

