In cases where the research is of therapeutic intent or is designed to investigate areas that would necessarily require certain populations who may not speak English, the researcher is required to make efforts to recruit and include non-English speaking individuals. However, there are studies in which it would be reasonable to limit subjects to those who speak English. Some examples include pilot studies, small unfunded studies with validated instruments not available in other languages, studies with numerous questionnaires, and some non-therapeutic studies which offer no direct benefit.

Response:

We will not enroll non-English speaking individuals. Enrollment in this study is not large (20 participants in total) and there is no reason to believe that the study would be withholding benefit from non-English speaking subjects.

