Subjects will come back within 2 weeks and will arrive after having fasted overnight (10 hours) at 7 to 7:30 am. They will then be randomized to either active tDCS or sham tDCS with block randomization (block size of 10). We will test urine pregnancy test to rule out pregnancy. Pregnant subject will be excluded from the study. We will also administer the three-factor eating questionnaire (Stunkard and Messick, 1985), which measures eating habits and attitudes toward food, weight and dieting, and a personality questionnaire, the Big Five (Costa and McCrae, 1989). We will evaluate cognitive responses to food with a 20-minute computerized task designed to engage the inhibitory control circuit when confronted with food stimuli, as well as engaging the other two components of executive function: working memory and cognitive flexibility. The task consists of 3 parts: a version of a Go/No-Go (GNG) task modified for food; an N-back memory task with food images, similar to a task used in a previous study; and a combined N-back and GNG task. In the food modified GNG task subjects have to press the space bar of a computer in response to pictures of low-calorie food, refraining from pressing when the pictures are of high-calorie food (25% of the time). In the N-back task, subjects will press the space bar when the picture displayed matches the picture displayed two images before. In the combined task, the subject will press the space bar when a picture of low-calorie food matches the picture displayed two images before, while refraining from pressing when a high-calorie food matches the picture displayed two images before.

Blood sample for BDNF and COMT gene test will be collected. We will also collect blood sample for plasma insulin and glucose level. We will download data from the continuous glucose monitor.

Subjects assigned to active tDCS group will receive 30 min of anodal tDCS delivered with a neuroConnVR DCSTIMULATOR device (neuroConn GmbH, Ilmenau, Germany), at a constant current of 2 mA (with a 30-second ramp at on- and offset) using two sponge electrodes soaked in a sterile 0.9% sodium chloride solution. The anode electrode will be placed over F3 (10–20 EEG system), with the cathode electrode placed over the contralateral supraorbital area, above the right eyebrow. This montage was used in a recent study that showed reduction of body weight and intake of soda and fat in a sample of obese subjects.

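### The analysis plan's only accuracy outcome, percentage correct, is not split by trial type; scored over all Go/No-Go trials it gives inhibition a quarter of the weight and should be replaced by a false-press rate for Aim 3

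*Combined protocol and SAP*

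**What the plan says.** Aim 3 (section 1.1) concerns executive function in the presence of food, in three components: "working memory, inhibitory control and a combination of both". It continues: "We will assess changes in accuracy and speed in the task under active tDCS versus sham tDCS". Section 2.1 lists the secondary endpoint only as "change in cognitive performance in response to food", with no metric.

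Section 10.1 (Visit 1) describes the task as "designed to engage the inhibitory control circuit when confronted with food stimuli", alongside working memory and cognitive flexibility. It has a food Go/No-Go part, an N-back part and a combined part. In the Go/No-Go part subjects press for low-calorie pictures, "refraining from pressing when the pictures are of high-calorie food (25% of the time". No trial share is given for the N-back or combined parts.

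Section 17.1 puts "reaction time and percentage correct response in computerized cognitive tests" into a generalized linear mixed model with time and intervention as predictors. No section defines a false-press (commission error) rate, No-Go accuracy, or scoring by trial type or task part.

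**The concern.** In a Go/No-Go task, inhibition shows in withholding the press on No-Go trials. Go trials chiefly measure attention and speed. A percentage correct taken over all trials mixes the two in a 75:25 ratio, with the smaller share on the construct that the aim names.

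Two consequences follow. First, the score has a high floor that says nothing about inhibition, because pressing at every picture earns most of the marks. Second, a subject who becomes more cautious may gain on No-Go trials and lose on Go trials, leaving the total flat. A null result on such a score could hide a change in inhibition towards high-calorie food. If pooling is not intended, the scoring is left open, and pooled, by-part or by-trial-type scores could be chosen after the data are seen.

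**Working it through.** The plan states no effect size, SD or power for this outcome, so there is no figure of its own to reproduce.

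**Inputs from the documents**
- No-Go share of Go/No-Go trials: 25%, hence a Go share of 75% (section 10.1).
- Total enrolment: 20 (sections 5.1 and 6.4).
- Randomization in blocks of 10 to two arms (section 10.1).

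**Assumed inputs (not in the documents)**
- Allocation 1:1, so 10 per arm; two-sided alpha 0.05; two-sample t-test.
- Between-subject SD of 12 to 15 points for No-Go accuracy and 3 to 5 points for Go accuracy.
- Correlation between the two, rho, from -0.3 to 0.3.
- True effect of 0.8 SD on No-Go accuracy and none on Go accuracy.

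**Step 1: score with no inhibition.** Pooled score = 0.75 × Go + 0.25 × No-Go.
- Always pressing, perfect Go accuracy: 0.75 × 100 + 0.25 × 0 = 75%.
- With Go accuracy of 95%: 71.25%. With 90%: 67.5%.

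**Step 2: change in percentage points.** With Go accuracy unchanged, a No-Go gain of 20 points moves the pooled score by 0.25 × 20 = 5 points. In raw points the shrinkage is always 1/0.25 = 4.

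**Step 3: change in SD units, which governs power.** The pooled score also has a smaller SD:

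SD_pooled² = (0.75 × SD_Go)² + (0.25 × SD_NoGo)² + 2 × 0.75 × 0.25 × rho × SD_Go × SD_NoGo

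d_pooled = 0.25 × 0.8 × SD_NoGo / SD_pooled

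Example with SD_NoGo = 12, SD_Go = 5, rho = 0: SD_pooled = √(3.75² + 3²) = 4.80, and d_pooled = 0.25 × 0.8 × 12 / 4.80 = 0.50.

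| SD_NoGo | SD_Go | rho | SD_pooled | d_pooled | Power, 10 per arm |
|---|---|---|---|---|---|
| 12 | 3 | -0.3 | 3.16 | 0.76 | 36% |
| 12 | 3 | 0 | 3.75 | 0.64 | 27% |
| 12 | 3 | 0.3 | 4.26 | 0.56 | 22% |
| 12 | 5 | -0.3 | 4.04 | 0.59 | 24% |
| 12 | 5 | 0 | 4.80 | 0.50 | 18% |
| 12 | 5 | 0.3 | 5.46 | 0.44 | 15% |
| 15 | 3 | -0.3 | 3.75 | 0.80 | 40% |
| 15 | 3 | 0 | 4.37 | 0.69 | 31% |
| 15 | 3 | 0.3 | 4.92 | 0.61 | 25% |
| 15 | 5 | -0.3 | 4.44 | 0.68 | 30% |
| 15 | 5 | 0 | 5.30 | 0.57 | 22% |
| 15 | 5 | 0.3 | 6.05 | 0.50 | 18% |

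Scored on No-Go trials alone, d = 0.8 gives 40% power. With the pooled score, d is 0.44 to 0.80 and power 15% to 40%. In SD units the effect shrinks by a factor of 1.0 (0.80/0.80) to 1.8 (0.80/0.44). One corner (SDs 15 and 3, rho = -0.3) shows no loss; the other eleven show some.

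**Step 4: limits.** The 25% share belongs to the Go/No-Go part. The weight of the withhold condition in the combined part, or of inhibition in a score over all three parts, cannot be computed.

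**The case against.** The strongest objection is that the plan never says accuracy is pooled. A reader might infer that overall percentage correct is the stated outcome. The text does not go that far: section 17.1 says neither overall nor pooled, it refers to tests in the plural, and Aim 3 lists the components separately. Percentage correct on No-Go trials alone would also fit the wording. This stands, and so the arithmetic above is conditional on pooled scoring. It does not remove the point, because no section selects the No-Go score and an unqualified percentage correct is most naturally read as correct responses over all trials of a test.

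A reader might also infer that any real effect is diluted fourfold. That holds for raw percentage points only, and only if Go accuracy does not change. In SD units the assumed inputs give 1.0 to 1.8. A negative correlation, which differences in caution between subjects would tend to produce, is where the loss is smallest.

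Two further objections carry weight. This is one of several secondary endpoints in a pilot of 20, and even the No-Go score has only 40% power for 0.8 SD, so a null result would say little under either scoring. Reaction time is analysed too, so slowing would not be wholly hidden. Both limit the importance of the point, but neither makes a pooled score a measure of inhibition.

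Finally, the documents do not say that responses are stored trial by trial. Section 18.1 A describes paper forms transferred to Excel. The sponsor has to confirm what the software exports.

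**Conclusion.** The point holds in a conditional form. Percentage correct is the only accuracy outcome in section 17.1 and is not defined by trial type or task part. On its plain reading, a Go/No-Go score of 75% is compatible with no inhibition at all (given perfect Go accuracy), and a No-Go change shows at a quarter of its size in percentage points if Go accuracy is unchanged. Those two results need only the 25% share and pooled scoring.

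The loss of power is uncertain. It ranges from none to a fall from 40% to 15%, and rests wholly on assumed SDs, correlation, effect size and 1:1 allocation. The documents do not support a single figure for it.

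The primary weight endpoint is unaffected. This is a cheap improvement to a secondary endpoint.

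**What to change.** First confirm that the task software exports responses by trial type, and obtain the number of No-Go trials per session. Then, in section 17.1:

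- Make the false-press rate on high-calorie No-Go trials the inhibitory-control outcome, modelled as a binomial count (false presses out of No-Go trials shown) within the generalized linear mixed model already planned.
- Do the same for the withhold condition of the combined task, that is, high-calorie pictures matching the one two images before.
- Report Go accuracy, Go reaction time and N-back accuracy as separate outcomes.

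If responses are available by trial type, this changes the wording of the analysis only, with no new visit or procedure. If the software gives only summary scores, its export must be changed as well. The downsides are that the No-Go rate rests on fewer trials and is noisier within a subject, which the binomial model reflects, and that there are a few more secondary outcomes to report.

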3.0 Background

3.1 Provide the scientific or scholarly background, rationale, and significance of the research based on the existing literature and how it will contribute to existing knowledge. Describe any gaps in current knowledge. Include relevant preliminary findings or prior research by the investigator.

Response:

Transcranial Direct current stimulation (tDCS) is a procedure in which a pair of electrode pads is applied over the scalp to deliver mild direct electric current to a specific area of the brain. It changes spontaneous firing rate of neurons underlying the pads[1], and the persistence of this modification in excitability of neurons can last up to 1 hour after the cessation of electric current[2]. This effect can be prolonged with repetitive stimulation over several consecutive days, most likely mediated by synaptic changes[3].

Left dorsolateral prefrontal cortex is a subregion of the prefrontal cortex considered to be involved in taste[4] and satiation[5]. Previous studies also demonstrated left dorsolateral prefrontal cortex in response to meal is different in lean men and women from obese subjects[6, 7], with obese subjects mounted a more significant response after meal. Therefore, this region of brain is a potential target for obesity intervention.

A recent study showed that tDCS inhibit craving for food[8]. Another prospective study of 9 obese subjects reveal that tDCS is associated with weight loss[9]. Our proposed study will explore the effect of tDCS on weight, appetite and glucose tolerance in long term (over 1 month period) and in a larger study population. We will apply sham tDCS as control. In sham tDCS, the duration of stimulation will be limited to 15 seconds instead of 30 minutes in the active tDCS group. According to previous study, subjects are the not able to differentiate sham from active tDCS [9].

Polymorphism of the catechol-O-methyltransferase (COMT) gene was found to interact with tDCS intervention and change its effect on higher level executive function[10]. The brain derived neurotrophic factor (BDNF) gene polymorphism was also shown to modulate the effect of tDCS on motor cortex plasticity [11]. Therefore, these genes can potentially alter the effect of tDCS on weight, appetite and cognitive response to food.

3.2 Include complete citations or references.

Response:

1. *Wassermann, E.M. and J. Grafman, Recharging cognition with DC brain polarization. Trends Cogn Sci, 2005. 9(11): p. 503-5.*

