Subjects assigned to sham tDCS group will receive 15 seconds of anodal tDCS delivered with a neuroConnVR DCSTIMULATOR device (neuroConn GmbH, Ilmenau, Germany), at a constant current of 2 mA (with a 30-second ramp at on- and offset) using two sponge electrodes soaked in a sterile 0.9% sodium chloride solution. However, they will stay at the research center for 30 minutes with electrodes on their scalp. Before starting the stimulation, a code will need to be entered into the tDCS machine which will decide whether a sham or active stimulation will be performed by the machine automatically in the next 30 minutes. At the beginning of the study, a code that is associated with either active stimulation or sham stimulation will be assigned to the subject based on the randomization. However, neither the subject or the operator of tDCS machine will know what does the code represent.

Visit 2: Subjects will come back next day to receive the second session of the same intervention.

Visit 3: Subjects will come back next day to receive the third session of the same intervention.

Visit 4: Subjects will come back next day to receive the fourth session of the same intervention.

Visit 5: Subjects will fast overnight (10 hours) and come back next morning at 7 to 7:30 AM to receive the fifth session of the same intervention. We will then measure body mass index, plasma insulin and glucose, appetite and cognitive function in response to food. Continuous glucose monitor will be reinstalled, and subjects will be instructed to wear it and document the time and types of food of every meal for at least 72 hours after this visit and 72 hours before the next visit. Subject will be instructed on how to insert and remove continuous glucose monitor again.

Visit 6: Subjects will fast overnight (10 hours) and come back next morning at 7 to 7:30 AM in 4 weeks after visit 5. We will measure body mass index, plasma insulin and glucose, appetite and cognitive function in response to food again. We will download data from the continuous glucose monitor. We will also ask if the subject believed that he/she received active or sham tDCS.

10.2 Describe what data will be collected.

NOTE: For studies with multiple data collection points or long-term follow up, consider the addition of a schedule or table in your response.

Response:

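### Section 17.1 does not tie the primary analysis to the primary endpoint: no arm-by-time term, visit-6 contrast or percent-change response is written

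*Combined protocol and SAP*

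**What the plan says.** Section 2.1 defines the endpoint: "Primary endpoints: change in weight, measured as a percentage of baseline body weight". Aim 1 in Section 1.1 fixes the time points: "We will measure weight of every participants at the beginning of the study and one month after the last session of tDCS". In Section 10.1 subjects have the fifth and last session at visit 5 and, for visit 6, "come back next morning at 7 to 7:30 AM in 4 weeks after visit 5". The primary comparison is therefore the arm difference in percent weight change from baseline to visit 6.

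The efficacy analysis is in Section 17.1: "Generalized linear mixed model will be applied to compare the difference in weight", together with the secondary outcomes. On the model terms: "Predicting variables include time in the study (baseline, visit 5 and visit 6) and type of intervention (active tDCS vs sham"). Baseline weight and other baseline variables are named there only as covariates to be examined for imbalance. Section 19.8 covers safety tests only. No other section adds an efficacy model.

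Weight is recorded at screening, visit 5 and visit 6 according to Section 10.2. Section 19.2 says height and weight are monitored at every visit.

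**The concern.** The endpoint sections and the analysis section describe different quantities. The first is a between-arm difference in percent change at one visit. The second, taken at its listed terms, is a between-arm difference in weight pooled over three visits. One of those visits is before treatment and one is on the day of the fifth session, when Section 10.1 says of the measurements after stimulation: "We will then measure body mass index, plasma insulin and glucose, appetite and cognitive function in response to food".

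The one-month horizon is what the study is meant to add. Section 3.1 says "Our proposed study will explore the effect of tDCS on weight, appetite and glucose tolerance in long term (over 1 month period"), and Section 17.2 contrasts this with earlier work: "previous shorter term study showed a small effect of tDCS on appetite and weight". An analysis that mixes an early effect with the one-month effect could shrink a real one-month effect, or show a difference when the effect has gone by then. A reader could not tell which term, visit or scale gives the planned primary result. In a 20-person pilot the main product is a usable estimate, so this matters even without a confirmatory claim.

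**Working it through.** The plan states no power, alpha, effect size or SD, so there is no figure of its own to reproduce. The first step is algebra. The later steps use assumed inputs.

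**Inputs.** From the documents: 20 participants (Section 5.1), blocks of 10 (Section 10.1), and time levels baseline, visit 5 and visit 6 (Section 17.1). Assumed: 10 per arm (no allocation ratio is stated), mean weight 100 kg, between-person SD 20 kg (range 15 to 25), within-person SD 1.5 kg (range 1 to 2), two-sided 5% tests, and independent normal errors within person.

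**1. What the listed terms estimate.** Let d5 and d6 be the arm differences in kg at visits 5 and 6. Randomisation makes the expected baseline difference 0. With complete data and a random intercept, the arm coefficient in a time + arm model is the difference between arms in subject means over the three visits:

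expected coefficient = (0 + d5 + d6)/3

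| d5 (kg) | d6 (kg) | Expected arm coefficient (kg) |
|---|---|---|
| 0 | -2 | -0.67 |
| -0.67 | -2 | -0.89 |
| -2 | -2 | -1.33 |
| -4 | -2 | -2.00 |
| -2 | 0 | -0.67 |

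If d5 lies between 0 and d6, the coefficient is one third to two thirds of d6. It equals d6 only when d5 is twice d6. In the last row it is not zero although nothing remains at visit 6. With missing visits or another covariance structure, the weights on the visits can change.

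**2. Its precision on raw weight.**

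SE = sqrt[(between SD² + within SD²/3) × 2/10]

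- SDs 20 and 1.5: sqrt[(400 + 0.75) × 0.2] = sqrt(80.15) = 8.95 kg.
- SDs 15 and 1: sqrt[(225 + 0.33) × 0.2] = 6.7 kg.
- SDs 25 and 2: sqrt[(625 + 1.33) × 0.2] = 11.2 kg.

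An expected coefficient of -0.89 kg against an SE of about 9 kg is 0.1 standard errors. In simulation the test rejects in about 5% of trials, as it would with no effect.

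**3. The arm-by-time contrast at visit 6, in kg.** Each person's change removes the between-person part:

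SE = sqrt[2 × 1.5² × 2/10] = sqrt(0.9) = 0.95 kg

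The estimate is unbiased for d6. With d5 = -0.67 and d6 = -2 it rejects in about 53% of simulated trials.

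**4. The analysis that matches the stated endpoint.** This is visit-6 percent change, adjusted for baseline weight. In the same setting the true difference is about -2.07 points, the SE is about 1.0 point, rejection is about 47% (29 to 82% over the assumed ranges), and 95% CI coverage is 95%. If percent change is instead averaged over visits 5 and 6 with the same adjustment, rejection is 31% and coverage of the visit-6 difference is 88%.

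**The case against.** The strongest reply is that *include* is not exhaustive. Baseline is a level of the time factor and the stated purpose is to compare arms, so a statistician would naturally fit arm-by-time. On that reading the model is unbiased for the visit-6 kg difference and rejects slightly more often than the percent-change ANCOVA (about 53% against 47%). This stands. A reader might infer that the trial is committed to a biased analysis, or that a mixed model is the wrong tool, and the documents support neither. What remains is that the interaction, the visit and the percent scale are written nowhere in the analysis plan, and that the listed terms alone do not give the endpoint.

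It is also fair that the one-third formula is conditional. Section 17.1 names no covariance structure, and the formula needs a random intercept and complete data.

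A third tempting step is to say that changing the response to percent change while keeping all three time levels still dilutes the effect, because the baseline row is zero for everyone. That is true as algebra, but no section describes such a fit, so the conclusion does not rest on it.

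Finally, this is a pilot with no power claim. That limits the consequence to an unclear or wrong primary estimate. It does not remove the need to say which estimate is primary.

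**Conclusion.** The point holds in this form: Section 17.1 leaves the primary estimate undefined, and the terms it lists, fitted alone, do not estimate the one-month percent change that Sections 1.1 and 2.1 make primary. That part rests on the text and on simple algebra. The sizes rest on assumed inputs: a coefficient one third to two thirds of the visit-6 effect when the visit-5 effect lies between zero and that effect, and an SE of about 9 kg (6.7 to 11.2) on raw weight.

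A reader might also infer that the correction always raises power. It does not. With a constant effect of -2 kg at both visits, a three-visit average of percent change (baseline set to zero) rejects in 62% of simulated trials, against 48% for the visit-6 analysis. That average, however, estimates -1.38 points rather than the visit-6 difference of about -2.07. The gain is the right estimate. This should be fixed, but it does not invalidate the design.

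**What to change.** State in Section 17.1 that the primary analysis is percent change in weight from baseline at visits 5 and 6, modelled with arm, visit, arm-by-visit and baseline weight, and that the primary estimate is the arm difference at visit 6 with its 95% CI. An ANCOVA of visit-6 percent change on arm and baseline weight has the same aim and would also do.

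Name the weight that serves as baseline. Section 10.2 lists screening, which can be up to two weeks before visit 1, while Section 19.2 implies that a visit-1 weight also exists.

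Use the same arm-by-visit structure for the secondary outcomes, each adjusted for its own baseline. A stated covariance structure, a baseline-weight-by-visit term and an exploratory arm-by-genotype estimate for Hypothesis 2 are optional additions.

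The cost is wording only: no new visits, participants or measurements. It should be settled before endpoint data are reviewed at the half-way point (Section 19.7).
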